3.0 STUDY OBJECTIVES

3.1. Intended Use and Indication

The intended use for TFNA is the following:

Intended Use: intended for the treatment of proximal femur and combinations of proximal and shaft fractures of the femur.

The indications of the TFNA are:

Short Nails (lengths 170 mm, 200 mm, 235 mm)

- Pertrochanteric fractures (31-A1 and 31-A2)
- Intertrochanteric fractures (31-A3)
- 235 mm nails are additionally indicated for high subtrochanteric fractures

Long Nails (lengths 260 mm - 480 mm)

- Pertrochanteric fractures (31-A1 and 31-A2)
- Intertrochanteric fractures (31-A3)
- Fractures of the trochanteric area (31-A1/A2/A3) with diaphyseal extension

- Combined fractures of the trochanteric area (31-A1/A2/A3) and the femoral shaft (32-A/B/C)
- Pathological fractures, including prophylactic use
- Malunions
- Nonunions

3.2. Objective

The primary objective of this study is to evaluate whether fracture union rate, evaluated 24 weeks after proximal femur fracture, for the investigational TFNA intramedullary nail is non-inferior to that for currently available control product PFNA-II in patients with proximal femur fractures.

4.0 STUDY DESIGN

This is a prospective, multicenter, randomized, controlled, two-arm, non-inferiority study which will be conducted in China, comparing the safety and the effectiveness of two intramedullary nails (the investigational group is TFNA and the control group is PFNA-II). Patients enrolled at each site will be randomized in a ratio of 1:1, i.e. one patient assigned to surgery implanted with TFNA for each patient assigned to PFNA-II. Separate block randomization schedules within each site will be used to ensure equal distribution of treatment and control patients. Up to 15 centers will be approved to participate in this study.

Patient will be clinically followed after surgery at 1, 6, 12 and 24 weeks. The data up to and including 24 week follow up visit will be used in determining the primary safety and effectiveness of the TFNA.

5.0 ENDPOINTS

5.1. Primary Endpoint

The primary endpoint is fracture union at 24 weeks postoperatively. Fracture union success is a composite endpoint; in order for an individual subject's surgery implanted with TFNA or PFNA-II to be considered successful he/she must satisfy all of the following criteria at 24 weeks:

- 1. No focal tenderness or lengthwise percussion pain, or abnormal movement
- 2. The frontal/lateral X-ray examination shows the vague or no fracture gap, or the continuous callus passing across the fracture line
- 3. No deformation or breakage is found in the test product

The primary endpoint analysis will be to demonstrate that the investigational device (TFNA) is non-inferior to the control device (PFNA-II) based the fracture union rate at the 24 week follow-up visit. Non-inferiority test will be conducted based on a one-sided 97.5% confidence interval for the difference in the fracture union rates at 24 weeks between the investigational and control groups.

5.2. Secondary Endpoints

The following secondary endpoints will be evaluated:

- Adverse events (type and frequency) for all adverse events will be compared for the investigational and control groups
- 24-week revision rate where revision is defined as removal of any component for any reason.
- 24-week reoperation rate is defined as secondary surgery at the fracture site(s) for any reason
- Clinical Outcomes
 - o SF-12
 - Harris Hip Score
 - o EQ-5D
- Radiographs: incidence of complications such as loosening or cut-out that require reoperation or revision

5.3 Safety

An overall summary of adverse events (AE) will be provided, including for each group the number and the percent of subjects with all AE, all serious AE, all related AE, and all AE by severity. In addition, all adverse events, serious, and non-serious adverse events will be summarized and tabulated by preferred term, both overall and by severity, by time period of onset, and by operative site

6.0 STUDY POPULATION

6.1. Subject Selection

The study will include 188 subjects with proximal femur fracture on a single limb requiring intervention that meet eligibility criteria and agree to participate in the study.

Subjects must meet ALL inclusion criteria and NO exclusion criteria.

6.2. Inclusion Criteria

Subjects will be included if ALL of the following inclusion criteria apply:

1) Age ≥18 years

2) Patients with unilateral proximal femur fractures that will be treated with intramedullary nail internal fixation

- 3) According to AO fracture classification, subjects with following fracture type:
 - a. Pertrochanteric (31-A1 and 31-A2)
 - b. Intertrochanteric (31-A3)
 - c. Trochanteric area (31-A1/A2/A3) with diaphyseal extension

4) Subject must be comfortable with speaking and understanding questions and responses in an available translated language for patient reported outcomes (PROs)

6.3 Exclusion Criteria

Subjects will be excluded if ANY of the following exclusion criteria apply:

- 1) Subject does not provide voluntary consent to participate in the study
- 2) The subject is a woman who is pregnant or lactating

3) Fractures where the operative treatment will occur more than three weeks after the primary injury

4) Patients with femoral head fractures and femoral neck fractures (AO classification 31-B and 31-C)

5) Pathological fracture (e.g., primary or metastatic tumor)

6) Serious soft tissue injury, judged by the investigator, will impact the union of the fracture, combined vascular injury, and combined osteofascial compartment syndrome

7) Multiple systemic injuries judged by researchers not suitable for enrollment, or orthopaedic fractures in other bones at three or more sites

8) Revision surgeries (for example, due to malunion, nonunion or infection)

9) Concurrent medical conditions judged by researchers not suitable for enrollment, such as: diabetes, metabolic bone disease, post-polio syndrome, poor bone quality, prior history of poor fracture healing, etc

10) Patients with anaesthetic and surgical contraindications

11) Patients known to be allergic to implant components

12) Patients who are currently using chemotherapeutics or accepting radiotherapy, use systematically corticosteroid hormone or growth factor, or long-term use sedative hypnotics (continuous use over 3 months) or non-steroidal anti-inflammatory drugs (continuous use over 3 months)

13) Intemperance judged by researchers not suitable for enrollment (e.g., excessive daily drinking or smoking, drug abuse);

14) Patients participated into other clinical trial in the previous 3 months;

15) Patients with bad compliance judged by researchers and cannot complete the test according to test scheme, such as schizophrenia and dementia.

7.0 STUDY PROCEDURES

7.1. Screening and Baseline Period

7.1.1. Patient Screening

A qualified member of the Institution's research team assigned to the study team will review the patient's medical history to screen for study eligibility. All patients meeting all inclusion criteria and no exclusion criteria will be invited to participate in the study.

7.1.2. Informed Consent

All potential patients must be consented prior to performing any study specific procedures. Once the Investigator has determined the patient's eligibility for the study, the background of the proposed study and the benefits and risks of the procedures and study must be explained to the patient. Only those patients who sign the site's Ethics Committee (EC) approved informed consent prior to participation are eligible to be in the study. Failure to provide written informed consent renders the patient ineligible for the study.

7.1.3. Screening and Baseline Assessments

To be performed for all patients prior to the procedure to ascertain eligibility:

- 1. Medical history
- 2. Inclusion and exclusion criteria
- 3. Physical Exam

7.1.4. Patient Enrollment

Sites will be required to maintain a record of patients screened for the study meeting general inclusion criteria who have signed the approved informed consent document.

Randomization will occur if the patient meets all inclusion criteria and does not meet any exclusion criteria.

Subjects who do not continue to meet eligibility criteria at this point are considered screening failures. The Investigator will document screening failures on the screening failure log, including reasons for failures. Once randomization is complete and a treatment arm is assigned, crossover between treatment arms will be considered as a major protocol violation.

If for some reason an enrolled subject does not receive a study device during their surgery he/she will be withdrawn postoperatively. This will be noted upon the end of study form.

Thus, patients will be considered enrolled into the study after:

- 1. The patient has met all of the inclusion and none of the exclusion criteria, and
- 2. Signed informed consent has been obtained.

7.1.5. Randomization and Treatment Assignment

Each patient will be assigned a unique patient identification number at screening that will be used to identify the patient throughout the study. Eligible patients will be randomized to study treatment or control group using a centralized computer-generated randomization system.

The study will be comprised of two (2) treatment groups: an investigational group (TFNA) and a control group (PFNA-II). Enrolled patients who meet inclusion and exclusion criteria will be randomized prior to the study procedure. Individual subjects will be randomized to one of two groups (TFNA or PFNA-II) in a 1:1 ratio. The plan is to accrue 94 subjects for each of the two groups.

7.2. Procedure

7.2.1. Instructions for Use

Preparation, handling and the implantation procedure must be performed in accordance with the Instructions for Use (IFU) provided within the implant packaging. An instrumentation system will be available for both investigational and control treatments. The surgeon should refer to the appropriate surgical technique manual for details on the use of the instrument system and implantation of the devices.

7.3. Post-Procedure

Subjects should be managed in accordance with institutional standards following the enrollment procedure including in-hospital and physiotherapy. Blood chemistry also will be documented. All adverse events (serious and non-serious) occurring during post-

operative hospitalization will be reported. Concomitant medications (prescription and non-prescription) will be collected.

7.4. Follow-up Period

For each clinic visit there is a required timeline for the visit, as shown in the Time & Events Table. For each of these visits, the data described in Table 8 must be collected.

	Enrollment			Foll	Follow-up		
	FU 1:	FU2:	FU3:	FU4:	FU5:	FU6:	
Event/Visit	Pre-Op	Surgery	1 week	6 weeks	12 weeks	24 weeks	
	-90 to 0		1 to 14				
	days from		days				
	day of		after	±2			
Required Timing	surgery	0	surgery	weeks	±2 weeks	±4 weeks	
The signing of the informed							
consent form	Х						
Inclusion/Exclusion criteria	Х						
Demographic data and medical							
history enquiry	Х						
Concise patient self-rated health							
measurement scale (SF-12v2)	Х				Х	Х	
EQ5D	Х				Х	Х	
Harris Hip Score					Х	Х	
Subject history	Х						
Urine pregnancy test ¹	Х						
Frontal and lateral X-ray of							
fracture sites	Х		Х	х	х	х	
Surgical reduction and							
intramedullary nail fixation		х					
Surgeon's evaluation on product							
operability during operation		х					
Wound healing assessment ²			Х				
Local physical examination	Х		Х	Х	Х	Х	
Concomitant drugs ³	Х	Х	Х	Х	Х	Х	
Adverse event		X4	Х	Х	Х	Х	
Serious adverse event		X4	Х	Х	Х	Х	
Blood chemistry	Х	X ⁵					

1. Urine pregnancy tests: women of childbearing age only.

2. Wound healing condition is assessed until wound healing.

3. Concomitant Drug Table should include only pain killers and anti-osteoporosis drugs.

4. Adverse events and serious adverse events should be recorded starting at the time of patient randomization.

5. Second Laboratory Test analyses performed during post-op recovery phase per site standard of care. The results closer to the time of surgery will be recorded.

Unscheduled Visits

If in between protocol required visits/telephone contacts, the site study team learns of any interventional treatment that a subject has undergone or study-related reportable adverse events, as defined in Section 8.0, the relevant information will be captured on the appropriate CRFs. All diagnostic radiographic films will be reviewed by the independent radiographic reviewer. All relevant source documentation required to assess the event will be maintained in the subject files and all relevant documentation required for event adjudication will be provided as requested by the Sponsor.

Clinical follow-up

The Investigator will be required to document clinical assessment in the medical and research source documents.

7.5. Blinding Procedures

Many medical records (source documents) documenting the patient's operative procedure, hospital stay and follow-up visits will not be blinded because implant labels identifying the implanted stems will be provided. As is common in device trials, it will not be possible to blind surgeon investigators or study staff because each group will be implanted with a different implant system, each of which is easily distinguished and has its own instrument set. Blinding of the independent radiographic reviewers and study staff also is not feasible because of small differences in design features that may be distinguished postoperatively (e.g., radiographs).

Blinding practices for this study will include the following:

Patients: Patients will be informed of the 1:1 randomization between the two devices, but will remain blinded as to which implant they actually received until after they have completed all study follow-up.

Implanting surgeon: It is not possible to blind the implanting physician due to his/her contact with the product labeling and IFU.

Independent Radiographic Reviewer (IRR): The IRR will not be blinded to the device implanted due to small differences that may be apparent in the radiographic images.

Medical Records: All medical records (source documents) documenting the implant procedure through hospital discharge and all follow-ups will not be blinded because implant labels identifying the implanted stems will be provided.

Monitors: Monitors will not be blinded because the detachable labels provided with the product identify the product and may be used in the study device accountability records and patient research file for the purpose of device accountability and source document validation.

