1.2.2 Comparison of TFNA and PFNA-II

The control device is Proximal Femoral Nail Antirotation II (PFNA-II). PFNA-II and TFNA have the same indications and can be used for treatment of pertrochanteric, intertrochanteric, high subtrochanteric fractures (Type 31-A). Both implants are contraindicated for treatment of femoral neck fractures. The overall design of both implants is that same in that they include a head element (TFNA: helical blade or screw; PFNA-II: screw) and distal locking screws. Both are manufactured from titanium alloys (TFNA: Titanium Molybdenum alloy; PFNA-II: Titanium Aluminum Niobium alloy).

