10.10.5 Analysis of the primary endpoint

In accordance with ICH guidance E9(²)the primary endpoint analysis will be based on the Per-Protocol set of patients for a comparison of the fracture union rates at Week 24 between TFNA and PFNA-II. Only patients in this analysis set with a known outcome for the primary endpoint will be analyzed.

The null hypothesis (TFNA is inferior to PFNA-II) will be rejected, and TFNA will be considered non-inferior to PFNA-II if the exact 97.5% upper one-sided confidence bound for the difference in fracture union rates between PFNA-II and TFNA at 24 weeks is less than non-inferiority margin, 10.0%.

Two sub-components of the primary endpoint at 24 weeks (radiographic outcome, and no deformation or breakage) will be compared between the two treatment groups.

Radiographic outcome, i.e. front/lateral X-ray films, will be assessed by the independent radiographic reviewer to determine if there are vague or fracture gap or continuous callus passing across the fracture line. The radiographic outcome will be summarized and compared at each follow up visit between the two treatment groups using Fishers exact test.

Similarly, the independent radiographic reviewer will also determine whether deformation or breakage of the implant has occurred. This outcome will be summarized between the two treatment groups at each follow up visit, as well.

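### Every professional assessor of the primary endpoint is unblinded by plan, and the reason given for unblinding the radiographic reviewer does not justify failing to conceal the allocation

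*Protocol*

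**What the plan says.** - **Radiographic reviewer.** Protocol Section 7.5 says "The IRR will not be blinded to the device implanted due to small differences that may be apparent in the radiographic images". Earlier in the section the same ground supports a claim of infeasibility: "Blinding of the independent radiographic reviewers and study staff also is not feasible because of small differences in design features". No other reason is given for the reviewer.
- **Site personnel.** Section 7.5 also says "it will not be possible to blind surgeon investigators or study staff because each group will be implanted with a different implant system". Monitors and medical records are unblinded too.
- **Patients.** They "will remain blinded as to which implant they actually received until after they have completed all study follow-up".
- **Who reads what.** Section 10.10.5: "Radiographic outcome, i.e. front/lateral X-ray films, will be assessed by the independent radiographic reviewer". The same reviewer decides whether the implant is deformed or broken. The remaining component in Section 5.1, "No focal tenderness or lengthwise percussion pain, or abnormal movement", comes from the local physical examination in the visit schedule, and Section 7.4 has the investigator document the clinical assessment.
- **SAP.** Section 7.3 derives the two imaging components from the week-24 X-ray record. It names no reader and adds no masking step.
- **Similarity of the devices.** Section 1.2.2 says "The overall design of both implants is that same".

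**The concern.** An independent reader protects against a site's expectations only if the reader does not share them. Here the plan makes lack of blinding a rule for the reader of two components, while the site examiners of the third are unblinded because they handle the implant. The ground offered is "small differences in design features that may be distinguished postoperatively". That describes a reader who might sometimes recognise the device. A rule that leaves the reader unblinded lets possible recognition become certain knowledge.

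The exposed judgement is the fracture line. Under SAP Section 7.3, calling it vague rather than clear can by itself satisfy the union component when callus is not continuous. With union assumed near 95% and a 10-point margin, a few borderline films can affect the conclusion.

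**Working it through.** **1. The plan's own figure.** Protocol 10.9 and SAP 6.2 give union 0.95 in both arms, margin 0.10 and power 80%. The Synopsis gives one-sided alpha 0.025.

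n per arm = (1.960 + 0.842)² × 2 × 0.95 × 0.05 / 0.10² = 74.6, so 75. Allowing 20% attrition: 75 / 0.80 = 93.75, so 94. Both figures reproduce. Masking the reader changes neither.

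**2. Who knows the arm, by component**

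| Component | Assessor | Status in Section 7.5 |
|---|---|---|
| Tenderness, percussion pain, abnormal movement | Site examiner, patient responding | Examiner unblinded, patient blinded |
| Fracture line or callus | Radiographic reviewer | Unblinded |
| Implant deformation or breakage | Radiographic reviewer | Unblinded |

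Neither document says that allocation, labels, the site's reading or the clinical findings are kept from the reviewer. Neither plans a check on whether the device can be recognised.

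**3. How recognisable are the devices?** The Study Components list in the Synopsis shows overlap: short nails of 9 to 12 mm, 170 and 200 mm lengths, and 125° and 130° angles exist in both systems. It also shows features of TFNA only: a screw head element, a 135° angle, and long nails of 11, 12 and 14 mm. Some films should therefore identify TFNA and others may not. Section 1.2.2 conflicts with this list, because it gives a screw as the PFNA-II head element where the Synopsis lists only a blade.

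**4. What a reading shift could do (illustration).** Assumptions, none from the documents: true union 85% TFNA and 95% PFNA-II, so that the difference lies exactly on the margin; 75 evaluable per arm; and a net shift s in the observed TFNA success rate, always in its favour.

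P(false non-inferiority) is the sum of Bin(x₁; 75, 0.85 + s) × Bin(x₂; 75, 0.95) over all (x₁, x₂) whose lower two-sided 95% limit for TFNA minus PFNA-II exceeds −0.10.

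| Shift s | Subjects of 75 | Share of the 15% true TFNA failures | Newcombe-Wilson, continuity-corrected | Wald |
|---|---|---|---|---|
| 0 | 0 | 0 | 1.5% | 3.7% |
| 2 points | 1.5 | 2/15 = 13% | 3.8% | 8.7% |
| 3 points | 2.25 | 3/15 = 20% | 6.0% | 12.9% |
| 5 points | 3.75 | 5/15 = 33% | 13.4% | 25.9% |

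The corrected Newcombe-Wilson limit is the SAP's sensitivity method (Section 7.3). The Wald limit is a plain unadjusted comparison. The SAP's primary site-adjusted CMH analysis and the protocol's exact bound were not modelled.

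**The case against.** The strongest reply is that the plan disclosed the problem and judged masking infeasible, with some reason. The nail is on every film, and implant integrity cannot be judged without looking at it. A screw head element would mark TFNA under the Synopsis list. Removing labels hides none of this. Reading the fracture line first does not hide it either, because fracture and nail share one image. This stands as a limit on what can be achieved: masking will be partial.

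The reply also bears on the numbers. The direction and size of the bias are assumed. The Wald column starts at 3.7% with no bias, so its later entries are not all due to reading. A 5-point shift needs a net one third of true TFNA failures to be called successes. Because continuous callus also satisfies the imaging component, and the other components must pass as well, the counts in the table are minimum numbers of misreadings. All of this stands.

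Three stronger readings are tempting and are not supported:

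- **That no part of the endpoint is free of knowledge of the arm.** Patients stay blinded, and tenderness and percussion pain depend partly on their responses. The reviewer may also be unable to tell the devices apart on some films.
- **That masking would cost almost nothing.** The documents give no cost. The modest step is concealing the allocation, which is less than full masking.
- **That the reviewer is sent the allocation or the site's reading.** The documents do not say what the reviewer receives. The defect is that nothing is withheld by rule.

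The reply does not show why imperfect masking should mean no concealment. Section 7.5 gives no further argument.

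**Conclusion.** The point holds in this form: every professional assessor of the primary endpoint is unblinded by plan, and the stated reason does not justify leaving the allocation unconcealed from the radiographic reviewer. This is a worthwhile correction to the design. It is not evidence that readings will be biased.

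The on-margin illustration shows sensitivity. With the corrected Newcombe-Wilson limit, a 2-point shift already takes the false-positive chance from 1.5% to 3.8%, above the nominal 2.5%. A reader might take the 13.4% or 25.9% for 5 points as an estimate of the trial's error rate. It is not one, because the documents give neither a misreading rate nor a direction.

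**What to change.** Replace the reviewer paragraph in Protocol Section 7.5, and the sentence calling blinding of the reviewer infeasible, with text to this effect:

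- The reviewer is not given the allocation, implant labels or part numbers, the site's reading, or clinical findings.
- Films are de-identified and presented without regard to arm.
- The fracture-line and callus reading is recorded and locked before implant integrity is assessed. This does not hide the nail, but it keeps the implant judgement from feeding back into the union reading.
- Optionally, the reviewer records which device he or she believes was used, and this is reported descriptively only. Do not repeat the non-inferiority comparison among films where the reviewer was unsure: that subset is selected after randomisation by device appearance and would be hard to interpret.

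Carry the same rules into the imaging instructions. Separately, reconcile the PFNA-II head element between the Synopsis and Section 1.2.2, since it bears on how recognisable the devices are.

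Cost: revised wording, de-identification and ordering of films that already go to the reviewer, and a locking step. No extra reader, patient procedure or subjects are needed. The downside is that masking remains incomplete for some films.
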